6.6.1.2. Primary Analysis using the Stratified Wilcoxon Rank Sum Test and Hodges-Lehmann Estimate

The primary analysis will be performed using the stratified Wilcoxon Rank Sum test for the FAS, stratified by baseline tafamidis use (yes vs. no). The analysis will be based on the following assumptions for missing data at Month 12:

1. Patients who die during the 12m-DB period (not due to COVID-19) or who have become unable to walk due to progression of ATTR amyloidosis by Month 12 and have missing data: Assuming that deaths observed in the study will likely be related to worsening of disease, the missing Month 12 6-MWT change from baseline will be imputed as the

worst 10th percentile change, capped by the worst possible change for the patient (ie, 0 – baseline 6-MWT).

2. Patients who have missing data due to other reasons will be imputed assuming data are MAR. Since the pattern of missing data within patients may be non-monotone, multiple imputation will be conducted separately by treatment arm and baseline tafamidis use group using the Markov Chain Monte Carlo (MCMC) method. For each treatment arm/baseline tafamidis use group, the imputation model will include type of amyloidosis (hATTR vs. wtATTR), NYHA class (I/II vs. III), age at randomization (<75 vs. ≥75), baseline NT-proBNP (≤3000 ng/L vs >3000 ng/L), baseline 6-MWT, and all calculated values of change from baseline in 6-MWT at pre-specified visits.

Missing values will be imputed 100 times to generate 100 complete datasets using the procedures described above. The stratified Wilcoxon Rank Sum test will be applied to each imputed dataset for the change from baseline in 6-MWT at Month 12. The Z scores estimated from the stratified Wilcoxon Rank Sum test fit to each imputed dataset will be combined by applying Rubin's rules,[Rubin 1996; Rubin 1987] using SAS PROC MIANALYZE to produce inferential results for the *p* value.

The effect size comparing treatment groups will be estimated using the stratified HL estimate (stratified by baseline tafamidis use) of the median difference in the change from baseline between patisiran and placebo, together with its 95% confidence interval (CI). The stratified HL is an estimate of the median value of all paired differences between observations in the patisiran versus placebo groups accounting for baseline tafamidis use, calculated using the imputed datasets. The calculation will be repeated for each imputed dataset, and the results will be combined by applying Rubin's rules,[Rubin 1996; Rubin 1987] using SAS PROC MIANALYZE to obtain the stratified HL estimate and corresponding 95% CI.

6.6.1.3. Sensitivity Analyses

Sensitivity analyses will be conducted using the following methods to assess the impact of missing data and the robustness of the primary analysis.

Sensitivity Analysis 1: Stratified Wilcoxon Rank Sum Test Including All Censored Data

A sensitivity analysis including all 6-MWT assessments (ie, not treating assessments that occur on or after the onset of a serious COVID-19 AE as missing) will be conducted using the same analyses as specified in Section 6.6.1.2.

Sensitivity Analysis 2: Stratified Wilcoxon Rank Sum Test with Control-based Imputation for Missing Data in Off-treatment Patisiran Patients

A sensitivity analysis will be performed using the stratified Wilcoxon Rank Sum test where missing data from off-treatment patisiran patients are imputed based on data from the placebo group. This accommodates situations where the missingness mechanism may be missing not at random (MNAR). The model will be based on the following assumptions for missing data at Month 12:

1. Patients who have missing data due to COVID-19, including patients who have missing assessments due to COVID-19, or who have a serious COVID-19 AE or who die due to COVID-19 prior to the Month 12 assessment will be imputed assuming data are MAR.

Under the hypothetical estimand of interest where the COVID-19 pandemic did not occur, these assessments should have been obtained with no COVID-19 impact. Missing data meeting these criteria will be imputed separately for each treatment arm and baseline tafamidis use group using multiple imputation (MI) estimated from all non-missing data collected within each group.

2. For patients who have missing data unrelated to COVID-19, who are alive through the 12m-DB period and who have not become unable to walk due to progression of ATTR amyloidosis by Month 12, the imputation will be performed by baseline tafamidis use (yes/no) separately based on different patterns described as below:
 - a. Placebo patients who have missing data: The missing data are considered MAR and will be imputed using multiple imputation (MI) estimated from placebo patients. The imputation is done regardless of whether a patient was on-treatment or discontinued treatment before the scheduled efficacy assessment.
 - b. Patisiran patients who have missing data while on treatment: Patients are expected to continue to show benefit from treatment similar to that observed at the scheduled time point. Therefore, missing data during the on-treatment period (within 60 days of their last dose) are considered MAR and will be imputed using MI estimated from all non-missing data collected on treatment from the patisiran arm.
 - c. Patisiran patients who have missing data after stopping their study treatment: Patients will no longer benefit from treatment in the future and will have trajectory similar to placebo patients after discontinuing treatment. Therefore, missing data after treatment discontinuation (more than 60 days after last dose of study drug) will be imputed using the data from placebo patients using the copy reference (CR) approach.
3. Patients who die during the 12m-DB period (not due to COVID-19) or who have become unable to walk due to progression of ATTR amyloidosis by Month 12 and have missing data: Assuming that deaths observed in the study will likely be related to worsening of disease, the missing Month 12 6-MWT change from baseline will be imputed as the worst 10th percentile change, capped by the worst possible change for the patient (ie, 0 – baseline 6-MWT). The imputation will be done for patients from both the patisiran and placebo arms.

Missing values will be imputed 100 times to generate 100 complete datasets using the procedures described above. The stratified Wilcoxon Rank Sum test (stratified by baseline tafamidis use) will be applied to each imputed dataset for the change from baseline in 6-MWT at Month 12. The Z scores estimated from the stratified Wilcoxon Rank Sum test fit to each imputed dataset will be combined by applying Rubin's rules, [Rubin 1996; Rubin 1987] using SAS PROC MIANALYZE to produce inferential results for the p value.

The effect size comparing treatment groups will be estimated using the stratified HL estimate (stratified by baseline tafamidis use) of the median difference in the change from baseline between patisiran and placebo, together with its 95% CI. The calculation will be repeated for each imputed dataset, and the results will be combined by applying Rubin's rules, [Rubin 1996;

[Rubin 1987](#)] using SAS PROC MIANALYZE to obtain the stratified HL estimate and corresponding 95% CI.

More details on the implementation of the control-based imputation for missing data are discussed in Appendix [9.1](#).

Sensitivity Analysis 3: MMRM Model

A sensitivity analysis will be performed using a REML-based MMRM approach. The outcome variable is the change from baseline in 6-MWT; the model includes baseline 6-MWT as a continuous covariate and treatment arm, visit (Month 6, Month 9 or Month 12), baseline tafamidis use (yes vs. no), type of amyloidosis (hATTR vs. wtATTR), age at randomization (<75 vs. ≥ 75 years), the treatment-by-visit interaction, the treatment-by-baseline tafamidis interaction, the visit-by-baseline tafamidis interaction, and the treatment-by-visit-by-baseline tafamidis interaction as fixed factors. Assessments obtained on or after the onset of a serious COVID-19 AE will be treated as missing and will be assumed as MAR.

An unstructured covariance structure will be used to model the within-patient errors. If the model fails to converge, the following covariance structures will be specified in sequence and the first to converge will be used:

1. Toeplitz
2. Autoregressive (1)
3. Compound symmetry

The Satterthwaite approximation will be used to estimate the degrees of freedom.

The primary comparison is the contrast (difference in LS means) between the patisiran and placebo arms at Month 12. The LS mean coefficients will be computed using the observed proportions of the categorical covariates (baseline tafamidis use, type of ATTR amyloidosis and age) in the FAS. The analysis will be implemented with SAS PROC MIXED.

The MMRM analysis assumes multivariate normality for the error term in the analysis model. This normality assumption will be assessed by inspection of residual plots along with a formal test for normality using the Shapiro-Wilk test.

6.6.1.4. Binary Analyses

Binary analysis for 6-MWT will be conducted on the observed 6-MWT data without imputation. The number and percentage of patients with a ≥ 0 meter increase in 6-MWT from baseline to Month 12 will be calculated for each treatment arm and compared between 2 arms using the Cochran-Mantel-Haenszel (CMH) test, stratified by baseline tafamidis use (yes vs. no). All patients with missing Month 12 data will be counted in the denominator with two exceptions: patients who are missing Month 12 data due to COVID-19 and patients with a 6-MWT assessment collected on or after the onset of a serious COVID-19 AE will be excluded.

6.6.1.5. Overview of Primary Endpoint Analyses

The planned analyses of the primary endpoint 6-MWT are summarized in [Table 2](#).

Table 2: Analysis of 6-MWT

Statistical Method
Primary analysis: Stratified Wilcoxon Rank Sum test
Sensitivity analysis 1: Stratified Wilcoxon Rank Sum test – including all available data without censoring
Sensitivity analysis 2: Stratified Wilcoxon Rank Sum test – implementing control-based imputation for missing data in off-treatment patisiran patients
Sensitivity analysis 3: MMRM
Other analysis: Binary analysis using stratified CMH

6.6.2. Secondary Endpoints

The secondary efficacy endpoints are specified in Section 3. To control overall type I error, the secondary endpoints will be tested in a hierarchical order as described in Section 5.7.

CV events will include all emergency/unplanned/non-elective hospitalizations after randomization adjudicated as being cardiovascular or being indeterminate, and all emergency/unplanned/non-elective visits after randomization that are adjudicated as being urgent HF visits. Deaths will include heart transplant and ventricular assist device placement, unless otherwise specified.

6.6.2.1. Change from Baseline at Month 12 in KCCQ-OS Score

6.6.2.1.1. Definition of Estimand

For the objective of evaluating the efficacy of patisiran compared with placebo on KCCQ-OS, the estimand is defined as follows:

- **Target patient population:** patients with hATTR or wtATTR amyloidosis with cardiomyopathy. Patients may or may not be taking tafamidis at study entry.
- **Treatment condition:** Patisiran 0.3 mg/kg or placebo administered as an IV infusion q3W (once every 3 weeks) with or without concomitant use of tafamidis.
- **Endpoint:** Change from baseline in KCCQ-OS at Month 12.
- **Population-level summary:** The least squares (LS) mean difference in the change from baseline in KCCQ-OS at Month 12 between the patisiran and placebo arms.

Intercurrent events and strategies: Intercurrent events include treatment discontinuation, serious COVID-19 AE, tafamidis drop-in, missing dose(s) due to COVID-19, and death. They require different handling strategies, which are described in Table 3 below.

Table 3: Intercurrent Event Strategies for the Primary Analysis of KCCQ-OS

Intercurrent Event	Handling Strategy
Treatment discontinuation (not due to death)	Treatment policy strategy: Intercurrent event is ignored; assessments obtained after treatment discontinuation will be included in analysis.

Intercurrent Event	Handling Strategy
Serious COVID-19 AE	Hypothetical strategy: Assessments obtained on or after the onset of a serious COVID-19 AE will be treated as missing and will be assumed as MAR. The goal is to estimate the scheduled visit values as if the patient had not been infected with COVID-19.
Tafamidis drop-in (ie, taking tafamidis for more than 28 days after randomization) in the subgroup of patients who were not on tafamidis at baseline	Treatment policy strategy: Intercurrent event is ignored; assessments obtained after tafamidis drop-in will be included in analysis.
Missing dose(s) due to COVID-19	Treatment policy strategy: Intercurrent event is ignored; assessments obtained after missing dose(s) due to COVID-19 will be included in analysis.
Death	Hypothetical strategy: Missing data due to death will be assumed as MAR.

6.6.2.1.2. Primary Analysis using MMRM for the Full Analysis Set

The change from baseline at Month 12 in KCCQ-OS will be analyzed using an MMRM model similar to the MMRM model for 6-MWT described in Section 6.6.1.3 while adjusting for baseline KCCQ-OS as a continuous covariate.

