2.2. Randomization Methodology

Using the interactive response system (IRS), patients will be randomized 1:1 to the patisiran or placebo arm. Randomization will be stratified by:

1. Baseline tafamidis (yes vs. no)
2. Type of amyloidosis (hATTR vs. wtATTR amyloidosis with cardiomyopathy)
3. New York Heart Classification (NYHA) Class I or II **and** age < 75 years vs. all other

Patients in the baseline tafamidis use category are defined as patients who are currently on tafamidis (for ≥ 6 months) with disease progression in the opinion of the investigator at baseline.

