5.7. Multiple Comparisons/Multiplicity

Formal statistical hypothesis testing will be performed on the primary and secondary efficacy endpoints with all tests conducted at the nominal 2-sided 0.05 significance level. The overall familywise error rate will be controlled at the 2-sided 0.05 significance level for the primary and secondary endpoints by a hierarchical ordering procedure. Endpoints will be tested in the following pre-specified hierarchy:

1. 6-minute walk test (6-MWT) change from baseline at Month 12
2. Kansas City Cardiomyopathy Questionnaire Overall Summary (KCCQ-OS) score change from baseline at Month 12
3. Composite endpoint of all-cause mortality, frequency of CV events (CV hospitalizations and urgent HF visits), and change from baseline in 6-MWT over the 12-month double-blind period
4. Composite endpoint of all-cause mortality and frequency of all-cause hospitalizations and urgent HF visits over the 12-month double-blind period in patients not on tafamidis at baseline

5. Composite endpoint of all-cause mortality and frequency of all-cause hospitalizations and urgent HF visits over the 12-month double-blind period in the overall population

There will be no multiplicity adjustment for exploratory endpoints.

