6.6.2.4.2. Primary Analysis

The composite endpoint of all-cause mortality and frequency of all-cause hospitalizations and urgent HF visits will be analyzed using a modified Andersen-Gill model stratified by baseline tafamidis use (yes vs. no), including treatment, type of amyloidosis (hATTR vs. wtATTR), baseline NYHA class (I/II vs. III), and age at randomization (<75 vs. ≥75 years) as covariates.

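### The KCCQ-OS MMRM and its pattern mixture ANCOVA omit NYHA class, which is part of the third randomisation factor and a covariate in both Andersen-Gill models; precision may be slightly lower, with no bias

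*SAP*

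**What the plan says.** Section 5.7 places "Kansas City Cardiomyopathy Questionnaire Overall Summary (KCCQ-OS) score change from baseline at Month 12" second in the fixed testing sequence, ahead of the win ratio and the two mortality and hospitalisation composites.

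Section 6.6.2.1.2 specifies its primary analysis by reference: the 6-MWT MMRM is carried over, "while adjusting for baseline KCCQ-OS as a continuous covariate". The model referred to is Sensitivity Analysis 3 in Section 6.6.1.3. Besides the baseline value, treatment and visit, its terms are "baseline tafamidis use (yes vs. no), type of amyloidosis (hATTR vs. wtATTR), age at randomization" and the interactions among treatment, visit and tafamidis. LS means are weighted by the "observed proportions of the categorical covariates (baseline tafamidis use, type of ATTR amyloidosis and age) in the FAS", which confirms that NYHA is not in the model. The ANCOVA in the KCCQ-OS pattern mixture analysis (Section 6.6.2.1.3) uses the same three categorical covariates.

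Section 2.2 stratifies randomisation by baseline tafamidis, amyloidosis type and a third, combined factor. One level of that factor is "New York Heart Classification (NYHA) Class I or II" together with age under 75; every other patient falls in the second level.

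The overall-population Andersen-Gill model (Section 6.6.2.4.2) includes "baseline NYHA class (I/II vs. III), and age at randomization" among its covariates, and the model for patients not on tafamidis at baseline (Section 6.6.2.3.2) does the same.

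**The concern.** A linear model for a continuous outcome should normally include the factors used to balance the arms. Stratified randomisation removes chance imbalance on those factors. If the model leaves a prognostic one out, its variation stays in the residual and the reported SE does not credit the balance achieved. The point estimate remains unbiased and the test becomes slightly conservative.

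Here the model carries the age part of the third factor but not the NYHA part. Age cannot stand in for it: a patient under 75 in NYHA III and one under 75 in NYHA I/II belong to opposite randomisation strata but share the same age term.

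KCCQ-OS gates three further endpoints, so even a small loss of power there carries down the sequence. The SAP treats NYHA as prognostic elsewhere (both Andersen-Gill models, the Poisson component models and the 6-MWT imputation model) and does not say why KCCQ-OS differs.

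**Working it through.** **1. Which confirmatory analyses use NYHA.**

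| Position | Endpoint | NYHA in the test or model? |
|---|---|---|
| 1 | 6-MWT, stratified Wilcoxon (6.6.1.2) | No; stratified by tafamidis only. NYHA is in the imputation model only |
| 2 | KCCQ-OS, MMRM (6.6.2.1.2) | No |
| 3 | Win ratio (6.6.2.2.2) | No; stratified by tafamidis only |
| 4 | Andersen-Gill, no baseline tafamidis (6.6.2.3.2) | Yes |
| 5 | Andersen-Gill, overall (6.6.2.4.2) | Yes |

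Two of the other four adjust for NYHA.

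**2. The plan's own power figure.** Section 5.1 gives power for 6-MWT only. The weighted difference is 0.7 × 33 + 0.3 × 20 = 29.1 m, stated as about 29 m, with SD 75 m and 150 patients per arm. SE = 75 × √(2/150) = 8.66 m, 29/8.66 = 3.349, and power = Φ(3.349 − 1.960) = 91.8%. The stated figure of more than 90% reproduces, but it does not bear on KCCQ-OS. The main SAP gives no KCCQ-OS SD, effect or power, and no NYHA correlation.

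**3. Effect of adding NYHA (assumption-based).** Let R² be the share of residual variance in KCCQ-OS change that NYHA (I/II vs III) explains beyond the terms already fitted. Take about 290 residual degrees of freedom, one of which is spent.

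- SE ratio f = √(1 − R²) × √(290/289)
- Power after = Φ((1.960 + z) / f − 1.960), with z = 0.842 for a starting power of 80% and 1.282 for 90%

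For R² = 0.10: f = 0.9487 × 1.0017 = 0.950. From 80%, 2.802/0.9503 − 1.960 = 0.988, which gives 83.8%.

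| Partial R² | Change in SE | Power from 80% | Power from 90% |
|---|---|---|---|
| 0 | +0.2% | 79.9% | 89.9% |
| 0.01 | −0.3% | 80.3% | 90.2% |
| 0.02 | −0.8% | 80.7% | 90.5% |
| 0.05 | −2.4% | 81.8% | 91.3% |
| 0.10 | −5.0% | 83.8% | 92.7% |

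The 80% and 90% starting values are also assumptions.

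**4. What reproduces the randomisation cell.** The combined factor is the product of two indicators, NYHA I/II and age under 75. Main effects of NYHA and age do not span a product. There are two ways to reproduce the cell exactly:

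- NYHA plus an NYHA-by-age term, which adds two parameters to the present model.
- The combined factor beside the existing age term, which adds one.

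**The case against.** The strongest reply is that the gain may be close to nothing. Baseline KCCQ-OS is already a covariate and is built from physical limitation, symptoms, quality of life and social limitation, much of what NYHA class grades. Age is fitted as well. A partial R² of 0.01 to 0.02 is credible and is worth well under one power point. This stands, and it limits the weight of the point.

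The covariate set is also stable: the MMRM omitted NYHA in the original SAP and in Amendment 1. Section 7.2 ties its update to the protocol, so a reason may exist in a document not seen here. Section 7.3 gives parsimony as the reason for dropping NYHA, but only for the echocardiographic and Norfolk ANCOVAs. Stability and a possible unseen reason do not show that the omission is better, and parsimony has little force for one parameter against about 300 patients. Section 6.6.4 does fit a KCCQ-OS model with NYHA as the subgroup term, but that is a subgroup analysis and not the confirmatory test.

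By Amendment 2.1, blinded 6-MWT data had been reviewed and regulatory comments received, so changing a confirmatory model has some prespecification cost. That is a reason to make the change blinded and documented.

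A reader might infer that KCCQ-OS is the one confirmatory analysis without NYHA. It is not: the Wilcoxon test and the win ratio also leave it out.

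**Conclusion.** The omission is real and unexplained, and it is minor. It causes no bias and does not threaten type I error. The cost is precision alone, and its size rests wholly on an assumed partial R². Over 0 to 0.10, the SE changes by +0.2% to −5.0%, and power by about −0.1 to +3.8 points from 80% or −0.1 to +2.7 points from 90%. The lower part of that range is quite possible.

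Three stronger readings are not supported:

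- **Adjustment can only help.** If NYHA adds nothing beyond the fitted terms, the SE rises by about 0.2%.
- **An NYHA main effect is the same as adjusting for the randomisation factor.** It is not, because the factor is a combined NYHA and age cell.
- **The single baseline slope across Months 6, 9 and 12 is a further error.** The model has no baseline-by-visit term, but that is a modelling preference, and the documents give nothing from which to size its effect.

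**What to change.** Before unblinding, amend Section 6.6.2.1.2 to add baseline NYHA class (I/II vs III) alongside age in the KCCQ-OS MMRM. If the randomisation cell is to be reproduced exactly, add the NYHA-by-age term as well, or use the combined factor, which Section 6.2 already tabulates at baseline. Make the same change to the pattern mixture ANCOVA in Section 6.6.2.1.3, and add the new term to the covariates whose observed proportions weight the LS means in both analyses.

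Because the MMRM is specified by reference to the 6-MWT model, write its terms out in full so that the addition is unambiguous. If the sponsor prefers to keep the present model, state the reason.

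The cost is SAP text, an entry in the Section 7 change log, and one or two parameters. NYHA class is already recorded, so no new data are needed.

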6.6.2.1.3. Sensitivity Analyses

Sensitivity analyses will be conducted using the following methods to assess the impact of missing data and the robustness of the primary analysis.

MMRM Model Including All Censored Data

A sensitivity analysis including all KCCQ-OS assessments, ie, not treating assessments that occur on or after the onset of a serious COVID-19 AE as missing, will be conducted using the same MMRM model as used for the primary analysis.

PMM Model

A sensitivity analysis using pattern mixture model (PMM) will be performed to assess the robustness of the primary MMRM results to the possible violation of the MAR assumption. The PMM accommodates situations where the missingness mechanism may be MNAR. The assumptions for missing data at Month 12 are the same as those specified in Section 6.6.1.3 with the exception of bullet 3, the imputation for patients who die during the 12m-DB period (not due to COVID-19). The revised bullet 3 is as follows:

- Patients who die during the 12m-DB period (not due to COVID-19) and have missing data: Assuming that deaths observed in the study will likely be related to worsening of disease, the missing Month 12 KCCQ-OS change from baseline will be imputed by taking random samples from the worst 10% KCCQ-OS changes observed during the 12m-DB period in the entire population, capped by the worst possible change for the

patient (ie, 0 – baseline KCCQ-OS). The imputation will be done for patients from both the patisiran and placebo arms.

Note that the PMM imputation rules for KCCQ-OS will not consider being unable to walk due to progression of ATTR amyloidosis in defining the missing data patterns since patients are still able to complete the KCCQ assessment in this scenario.

Missing values will be imputed 100 times to generate 100 complete datasets using the procedures described above. An analysis of covariance (ANCOVA) model will be fit to each imputed dataset for the change from baseline in KCCQ-OS at Month 12. The ANCOVA model will include baseline KCCQ-OS as a continuous covariate and treatment arm, baseline tafamidis use (yes vs. no), type of ATTR amyloidosis (hATTR vs. wtATTR), age at randomization (<75 vs. ≥ 75), and the treatment-by-baseline tafamidis interaction as covariates. The LS mean coefficients will be computed using the observed proportions of the categorical covariates (baseline tafamidis use, type of ATTR amyloidosis and age) in the FAS. The LS mean and standard error of the mean (SEM) estimated from the ANCOVA model fit to each imputed dataset will be combined by applying Rubin's rules, [Rubin 1996; Rubin 1987] using SAS PROC MIANALYZE to produce inferential results including the treatment difference in LS means, 95% CI for the treatment difference, and the p value.

